### **13.1.2.3 Reporting Serious Adverse Events**

The investigator is responsible for notifying the sponsor within 24 hours of identifying an SAE, regardless of the presumed relationship to the investigational study drug. The SAE Form will be completed for new/initial events as well as to report follow-up information on previously reported events. Investigators are asked to report follow-up information as soon as it becomes available to ensure timely reporting to health authorities.

Please send completed SAE Forms to Vertex GPS via:

Email: [[contact]](mailto:[contact]) (preferred choice)

Fax: [name]

Contact Telephone: [name]

### **13.1.2.4 Expedited Reporting and Investigator Safety Letters**

Vertex, as study sponsor, is responsible for reporting suspected, unexpected, serious adverse reactions (SUSARs) involving the study drug(s) to all regulatory authorities and participating investigators in accordance with ICH Guidelines and/or local regulatory requirements, as applicable. In addition, Vertex, or authorized designee, will be responsible for the submission of safety letters to central IECs.

It is the responsibility of the investigator or designee to promptly notify the local IRB/local IEC of all unexpected serious adverse drug reactions involving risk to human subjects.

## **13.2 Administrative Requirements**

### **13.2.1 Ethical Considerations**

The study will be conducted in accordance with the current ICH GCP Guidelines, which are consistent with the ethical principles founded in the Declaration of Helsinki, and in accordance with local applicable laws and regulations. The IRB/IEC will review all appropriate study documentation to safeguard the rights, safety, and well-being of the subjects. The study will only be conducted at sites where IRB/IEC approval has been obtained. The protocol, Investigator's Brochure, sample ICF, advertisements (if applicable), written information given to the subjects, safety updates, annual progress reports, and any revisions to these documents will be provided to the IRB/IEC by the investigator or Vertex, as allowable by local applicable laws and regulations.

### **13.2.2 Subject Information and Informed Consent**

After the study has been fully explained, written informed consent will be obtained from the subject's parent or legal guardian before study participation. The method of obtaining and documenting the informed consent and the contents of the consent will comply with ICH GCP and all applicable laws and regulations and will be subject to approval by Vertex or its designee.

### **13.2.3 Investigator Compliance**

No modifications to the protocol will be made without the approval of both the investigator and Vertex. Changes that significantly affect the safety of the subjects, the scope of the investigation, or the scientific quality of the study (i.e., efficacy assessments) will require IRB/IEC notification before implementation, except where the modification is necessary to eliminate an apparent immediate hazard to human subjects. Vertex will submit all protocol modifications to the required regulatory authorities.

When circumstances require an immediate departure from procedures set forth in the protocol, the investigator will contact Vertex to discuss the planned course of action. If possible, contact will be made before the implementation of any changes. Any departures from the protocol will be fully documented in the source documentation and in a protocol deviation log.

#### **13.2.4 Access to Records**

The investigator will make the office and/or hospital records of subjects enrolled in this study available for inspection by Vertex or its representative at the time of each monitoring visit and for audits. The records will also be available for direct inspection, verification, and copying, as required by applicable laws and regulations, by officials of the regulatory health authorities (FDA and others). The investigator will comply with applicable privacy and security laws for use and disclosure of information related to the research set forth in this protocol.

#### **13.2.5 Subject Privacy**

To maintain subject confidentiality and to comply with applicable data protection and privacy laws and regulations, all CRFs, study reports, and communications relating to the study will identify subjects by assigned subject numbers, and access to subject names linked to such numbers shall be limited to the site and the study physician and shall not be disclosed to Vertex. As required by applicable laws and regulations in the countries in which the study is being conducted, the investigator will allow Vertex and/or its representatives access to all pertinent medical records to allow for the verification of data gathered in the CRFs/SAE forms and the review of the data collection process. The FDA and regulatory authorities in other jurisdictions, including the IRB/IEC, may also request access to all study records, including source documentation, for inspection.

For sites participating in the study in the US, and in accordance with the Health Insurance Portability and Accountability Act and associated regulations (“HIPAA”), an executed HIPAA authorization shall be obtained by the site from each subject (or the legal representative of the subject) before research activities may begin. Each HIPAA authorization shall comply with all HIPAA requirements including authorization allowing the site access to and use of the subject’s personally identifiable health information, authorization for the site to disclose such information to Vertex, the FDA, and other parties requiring access under the protocol, and statements as to the purpose for which such information may be used and for how long.

#### **13.2.6 Record Retention**

The investigator will maintain all study records according to ICH GCP guidelines and/or applicable local regulatory requirement(s), whichever is longest, as described in the Clinical Trial Agreement. If the investigator withdraws from the responsibility of keeping the study records, custody will be transferred to a person willing to accept the responsibility, and Vertex will be notified.

#### **13.2.7 Study Termination**

At any time, Vertex may terminate this study in its entirety or may terminate this study at any particular site. In addition, for reasonable cause, either the investigators or their IRBs/IECs may terminate the study at their center.

Conditions that may lead to reasonable cause and warrant termination include, but are not limited to:

- Subject or investigator noncompliance
- Unsatisfactory subject enrollment
- Lack of adherence to protocol procedures
- Lack of evaluable and/or complete data
- Potentially unacceptable risk to study subjects
- Decision to modify drug development plan
- Decision by the FDA or other regulatory authority

Written notification that includes the reason for the clinical study termination is required.

### **13.3 Data Quality Assurance**

Vertex or its designated representative will conduct a study site visit to verify the qualifications of each investigator, inspect clinical study site facilities, and inform the investigator of responsibilities and procedures for ensuring adequate and correct study documentation.

The investigator is required to prepare and maintain adequate and accurate case histories designed to record all observations and other data pertinent to the study for each study participant. Study data for each enrolled subject will be entered into a CRF by study site personnel using a secure, validated, web-based electronic data capture (EDC) application. Vertex will have read-only access to site-entered clinical data in the EDC application.

Instances of missing, discrepant, or uninterpretable data will be queried with the investigator for resolution. Any changes to study data will be made to the CRF and documented in an audit trail, which will be maintained within the clinical database.

### **13.4 Monitoring**

Monitoring and auditing procedures developed or approved by Vertex will be followed to comply with GCP guidelines. On-site checking of the CRFs/SAE Forms for completeness and clarity, cross-checking with source documents, and clarification of administrative matters will be performed.

The study will be monitored by Vertex or its designee. Monitoring will be done by personal visits from a representative of Vertex, or designee (study site monitor), who will review the CRFs/SAE Forms and source documents. The study site monitor will ensure that the investigation is conducted according to the protocol design and regulatory requirements.

### **13.5 Electronic Data Capture**

Vertex will provide the study sites with secure access to and training on the EDC application sufficient to permit study site personnel to enter or correct information in the CRFs on the subjects for which they are responsible.

A CRF will be completed for each enrolled study subject. It is the investigator's responsibility to ensure the accuracy, completeness, clarity, and timeliness of the data reported in the subject's CRF. Source documentation supporting the CRF data will indicate the subject's participation in the study and will document the dates and details of study procedures, AEs, other observations, and subject status.

The investigator, or designated representative, will complete the CRF as soon as possible after information is collected.

The audit trail entry will show the user's identification information and the date and time of any correction. The investigator will provide formal approval of all the information in the CRFs, including any changes made to the CRFs, to endorse the final submitted data for the subjects for whom the investigator is responsible.

Vertex will retain the CRF data and corresponding audit trails. A copy of the final archival CRF in the form of a CD or other electronic media will be placed in the investigator's study file.

## **13.6 Publications and Clinical Study Report**

### **13.6.1 Publication of Study Results**

Any and all scientific, commercial, and technical information disclosed by Vertex in this protocol or elsewhere will be considered the confidential and proprietary property of Vertex. The investigator shall hold such information in confidence and shall not disclose the information to any third party except to such of the investigator's employees and staff as have been made aware that the information is confidential and who are bound to treat it as such and to whom disclosure is necessary to evaluate that information. The investigator shall not use such information for any purpose other than determining mutual interest in performing the study and, if the parties decide to proceed with the study, for the purpose of conducting the study.

The investigator understands that the information developed from this clinical study will be used by Vertex in connection with the development of the study drug and other drugs and diagnostics, and therefore may be disclosed as required to other clinical investigators, business partners and associates, the FDA, and other government agencies. The investigator also understands that, to allow for the use of the information derived from the clinical study, the investigator has the obligation to provide Vertex with complete test results and all data developed in the study.

No publication or disclosure of study results will be permitted except under the terms and conditions of a separate written agreement between Vertex and the investigator and/or the investigator's institution.

### **13.6.2 Clinical Study Report**

A clinical study report, written in accordance with the ICH E3 Guideline, will be submitted in accordance with local regulations.

2 MODIFICATIONS

2.1 Modifications to the Approved Clinical Study Protocol

In calculating normalized measures of growth (weight-for-age z-scores, length-for-age z-scores, and weight-for-length-for-age z-scores), WHO reference standards are used instead of CDC reference standards, per CDC recommendations. The reference for z-scores has been updated accordingly.

Per Administrative Letter dated 31 October 2017, in the Schedule of Assessments tables for same-day and gap-transition subjects from Study 124 Part B, an ‘X’ was inadvertently omitted from the row “12-lead ECGs” for the column “Weeks 12, 36, 60, and 84 (+/- 7 Days)” under “Treatment Period (Day 1 through Week 96).” Data from 12-lead ECGs at these visits will be presented.

Per Administrative Letter dated 07 October 2022, text identified below is revised to clarify that the Follow-up Ophthalmologic Examination (OE) is not required for subjects who rolled over from Study VX15-770-124 and who initiate treatment with commercially available ivacaftor, because safety information for these patients will be collected and reported as part of the post-marketing process. This clarification is being provided to maintain consistency with the Safety Follow-up visit for these subjects, which is not required for the same reason. Text identified below is copied from the indicated section of the protocol with clarifying text provided in italics and deleted text in strikethrough font.

Section 2 Protocol Synopsis Study Design

Subjects who receive commercially available ivacaftor will be discontinued from study drug dosing and will complete the ETT Visit ~~and the Follow-up OE~~; the Safety Follow-up Visit *and 24-Week Follow-up OE* will not be required

Section 9.1.1.4 Ivacaftor Arm Follow-up Ophthalmologic Examination (All Subjects)

There will be a Follow-up OE 24 weeks + 14 days after the last dose of ivacaftor for all subjects *except for subjects who initiate treatment with commercially available ivacaftor within 3 weeks of the final scheduled treatment visit or ETT Visit.*

Section 9.1.1.5 Ivacaftor Arm Early Termination of Treatment (All Subjects)

Subjects who receive commercially available ivacaftor will be discontinued from ivacaftor dosing and will complete the ETT Visit ~~and Follow-up OE~~; the Safety Follow up Visit *and Follow-up OE* will not be required.

Section 9.7 Removal of Subjects

During the course of study conduct, if ivacaftor is approved and available for the treatment of CF in populations enrolled in this study, and if a subject chooses to move onto commercially available ivacaftor, the ETT Visit (Section 9.1.1.5) will be completed before dosing with commercial drug begins, and the Safety Follow-up Visit and Follow-up OE will not be required.

Table 3-1 Footnote “a”

The ETT Visit is to be scheduled as soon as possible after the last dose of ivacaftor. If the ETT Visit occurs 3 weeks or later after the last dose of ivacaftor, the Safety Follow up Visit will not be required. Subjects who elect to receive commercially available ivacaftor will be discontinued from ivacaftor dosing and will complete the ETT Visit ~~and Follow-up OE.~~

Table 3-1 Footnote “b”

For subjects who elect to receive commercially available ivacaftor, the Safety Follow-up Visit *and Follow-up OE* will not be required.

Additional Clarifications

The following are provided to correct minor inconsistencies:

Table 3-1 Footnote “d”

Study Drug Dose Determination is not to be performed at the Week 96 Visit because it is the final visit of the treatment period.

Tertiary Endpoint “weight-for-length-for-age z-score”

The term “weight-for-length-for-age z-score” is not the appropriate name for this endpoint. The correct name is “weight-for-length z-score” in the following sections of the protocol: Sections 2 Synopsis (Assessments); 7.1.3 Tertiary Endpoints; 9.2.3 Rationale for Study Assessments (Measures of Nutritional Status); 11.5.1 Measures of Nutritional Status; and 12.3.3.3 Analysis of Tertiary Variables.

In addition, the final analysis will be based on the combined subjects from Study 124 Parts B and A/B, and subjects not from Study 124 Parts B and A/B.

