For the Ivacaftor Arm, the TE period will include the time period starting from the first dose date of the study drug in the current study to the Safety Follow-up Visit, or the last dose date + 28 days for subjects who do not have a Safety Follow-up Visit. The TE period will be used for safety analyses unless specified otherwise.

Unscheduled visits: Unscheduled visit measurements will be included in analysis as follows:

- In scheduled visit windows per specified visit windowing rules
- In the derivation of baseline/last on-treatment measurements.
- In the derivation of maximum/minimum on-treatment values and maximum/minimum change from baseline values for safety analyses.
- In individual subject data listings as appropriate.

Visit windowing rules: The analysis visit windows for protocol-defined visits in the Ivacaftor Arm are provided in Appendix B. The windows will be applied using the following rules for both scheduled and unscheduled visits. If no measurement is available within a visit window, the assessment will be considered missing for the visit. If there is more than one measurement available within the same visit window, the following rules will be used:

- For all safety parameters, if there are multiple measurements within a visit window, then 1) the record closest to the target day will be used, with the exception of the threshold analysis in which the worst record will be used; 2) if there are multiple records within the same distance of the target day, the latest record will be used; or 3) the Safety Follow-Up (SFU) visit will not be windowed; instead, the nominal visit will be used in relevant analyses.
- For all efficacy parameters, if there are multiple measurements within a visit window, the record at the scheduled visit will be used. Otherwise,
 - If there are no measurements at the scheduled visit, then the record closest to the target day will be used;

- If there are multiple records with the same distance to the target day, the latest record will be used.
- Assessments at the early treatment termination (ETT) visit will follow the windowing rules for regular visits, with the exception of the ETT visit occurs 21 days or later after the last dose, which will be treated as SFU visit.

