8.4.3 Electrocardiogram

For treatment-emergent ECG measurements, a summary of raw values and change from baseline values will be provided by visit for the following standard 12-lead ECG measurements: RR (ms), HR (bpm), PR (ms), QRS duration (ms), QRS axis (degrees), QT (ms), and QT corrected for HR intervals [QTcF (ms)].

The number and percentage of subjects meeting at least 1 threshold analysis criterion during the TE period for the Treatment Period will be summarized. The threshold analysis criteria are provided in Appendix E.

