	Week 72	504	[463, 546]
	Week 84	588	[547, 630]
	Week 96	672	[631, max(686, Date of Week 96 + 14)]
	Safety Follow-up Visit	NA	Use nominal visit
Standard 12-Lead ECG	Baseline	Not applicable	parent study baseline
	Week 24	168	[2, 252]
	Week 48	336	[253, 420]
	Week 72	504	[421, 588]
	Week 96	672	[589, max(686, Date of Week 96 + 14)]
	Safety Follow-up Visit	NA	Use nominal visit
Ophthalmologic Exam	Baseline	Not applicable	parent study baseline
	Week 24	168	[2, 252]
	Week 48	336	[253, 420]
	Week 72	504	[421, 588]
	Week 96	672	[589, max(686, Date of Week 96 + 14)]
	24-Week Follow-up OE	NA	Use nominal visit
Efficacy Assessments			
Weight Length Weight-for-length BMI Weight-for-age z-score Length-for-age z-score Weight-for-length z-score BMI-for-age z score	Baseline	Not applicable	parent study baseline
	Week 12	84	[2, 126]
	Week 24	168	[127, 210]
	Week 36	252	[211, 294]
	Week 48	336	[295, 378]
	Week 60	420	[379, 462]
	Week 72	504	[463, 546]
	Week 84	588	[547, 630]
	Week 96	672	[631, max(686, Date of Week 96 + 14)]
	Safety Follow-up Visit	NA	Use nominal visit ^c

Fecal elastase-1 Fecal calprotectin Sweat chloride Qualitative Microbiology Multiple Breath Washout	Baseline	Not applicable	parent study baseline
	Week 24	168	[2, 252]
	Week 48	336	[253, 420]
	Week 72	504	[421, 588]
	Week 96	672	[589, max(686, Date of Week 96 + 14)]

^a Visit name is used to report data in tables, listings and figures.

^b Target day time point per protocol is predose, except for ECG measurements.

^c Per section 8.1, it will remain as the SFU if it goes beyond the upper boundary of the window for the last scheduled visit.

Table 11-5 Analysis Visit Windows for Safety and Efficacy Assessments – IVA-naïve subjects (Subjects Not From Study 124 Part B or Part A/B)

Assessment	Visit ^a	Target Study Day ^b	Analysis Visit Window (in study days)
Safety Assessments			
Serum Chemistry	Baseline	1	≤1
	Week 2	14	[2, 35]
	Week 8	56	[36, 70]
	Week 12	84	[71, 105]
	Week 18	126	[106, 147]
	Week 24	168	[148, 210]
	Week 36	252	[211, 294]
	Week 48	336	[295, 378]
	Week 60	420	[379, 462]
	Week 72	504	[463, 546]
	Week 84	588	[547, 630]
	Week 96	672	[631, max(686, Date of Week 96 + 14)]
Safety Follow-up Visit	NA	Use nominal visit	
Hematology	Baseline	1	≤1
	Week 4	28	[2, 42]
	Week 8	56	[43, 70]
	Week 12	84	[71, 105]
	Week 18	126	[106, 147]
	Week 24	168	[148, 210]
	Week 36	252	[211, 294]
	Week 48	336	[295, 378]
	Week 60	420	[379, 462]
	Week 72	504	[463, 546]
	Week 84	588	[547, 630]

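### SAP 2.1 promises the rollover ECGs at Weeks 12, 36, 60 and 84, but Table 11-4 has no windows for them, so half the scheduled on-treatment ECGs miss the by-visit summary or appear under the wrong visit

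*SAP*

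**What the plan says.** SAP 2.1 reports that, under an administrative letter of 31 October 2017, an X "was inadvertently omitted from the row" for 12-lead ECGs in the Weeks 12, 36, 60 and 84 column, for both same-day and gap-transition subjects from Study 124 Part B. It then commits: "Data from 12-lead ECGs at these visits will be presented".

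SAP 8.4.3 defines the main ECG output: "a summary of raw values and change from baseline values will be provided by visit for the following standard 12-lead ECG measurements". SAP 8.1 governs which record enters it. For safety parameters with several records in one window, "the record closest to the target day will be used, with the exception of the threshold analysis in which the worst record will be used"; ties go to the latest record. The windows apply to scheduled and unscheduled visits alike, and for ECGs only the Safety Follow-up Visit keeps its nominal name. A footnote to Table 11-4 says that the analysis visit name is the label used in all outputs, listings included.

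For rollover subjects, the "Standard 12-Lead ECG" block of Table 11-4 contains only these on-treatment rows:

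| Analysis visit | Target day | Window (study days) |
|---|---|---|
| Week 24 | 168 | 2 to 252 |
| Week 48 | 336 | 253 to 420 |
| Week 72 | 504 | 421 to 588 |
| Week 96 | 672 | 589 to max(686, date of Week 96 + 14) |

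The rollover schedules in SAP Appendix A (Tables 11-1 and 11-2) also still lack the X.

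**The concern.** The correction announced in SAP 2.1 did not reach the table that drives the programming. A programmer who follows Table 11-4 has nowhere to put a rollover ECG from Week 12, 36, 60 or 84 except in the window of a different visit, where it competes with the ECG that belongs there.

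Two consequences follow for a component of the primary safety endpoint. The by-visit summaries of raw values and change from baseline would omit visits that the SAP says it will present. And because SAP 2.1 and 8.1 pool rollover and IVA-naïve subjects, the ECG rows for Weeks 12, 36, 60 and 84 would contain IVA-naïve subjects only, while Weeks 24, 48, 72 and 96 contain both groups. A reader following QTcF over time would see the population change from row to row with no explanation.

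**Working it through.** The plan states no figure to reproduce; the analysis is descriptive. The check assigns each scheduled ECG to a window and applies the selection rule.

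**Inputs.** Scheduled day = 7 × week, giving days 84, 168, 252, 336, 420, 504, 588 and 672. The visit allowance is ±7 days (protocol Tables 3-1 and 3-2), so each visit has 15 permitted days. Windows are from SAP Table 11-4 and the selection rule from SAP 8.1.

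**Step 1: assign the intermediate visits.**

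| Visit | Scheduled day | Permitted days | Window on scheduled day | Split of the 15 permitted days |
|---|---|---|---|---|
| Week 12 | 84 | 77–91 | Week 24 | 15 in Week 24 |
| Week 36 | 252 | 245–259 | Week 24 | 8 in Week 24, 7 in Week 48 |
| Week 60 | 420 | 413–427 | Week 48 | 8 in Week 48, 7 in Week 72 |
| Week 84 | 588 | 581–595 | Week 72 | 8 in Week 72, 7 in Week 96 |

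Days 252, 420 and 588 are exactly the upper bounds of the Week 24, 48 and 72 windows. An ECG one day late therefore changes label. The Week 24, 48, 72 and 96 ECGs fall in their own windows on all 15 permitted days.

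**Step 2: distance from the window's target.**
- Week 12 against day 168: from 168 − 91 = 77 to 168 − 77 = 91 days.
- Week 36 in the Week 24 window: from 245 − 168 = 77 to 252 − 168 = 84 days. In the Week 48 window: from 336 − 259 = 77 to 336 − 253 = 83 days. Weeks 60 and 84 give the same distances by symmetry.
- A 24-weekly ECG within its allowance is at most 7 days from target.

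Since 77 > 7, the intermediate ECG is never selected when the 24-weekly ECG in that window exists. Retention in the by-visit summary is 4 of 8 scheduled post-Day-1 ECGs, or 50%.

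**Step 3: 24-weekly ECG missing.** Suppose Week 24 is missing and Weeks 12 and 36 are on their scheduled days. Their distances are 168 − 84 = 84 and 252 − 168 = 84. The tie goes to the later record, so the Week 36 ECG is reported as Week 24. If Week 36 is also missing, the day-84 ECG is reported as Week 24, 12 weeks early.

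**Step 4: is the omission deliberate?** Table 11-4 uses 12-weekly windows for rollover chemistry, hematology and vital signs, which are collected at these same visits. The IVA-naïve window table (Table 11-5 in Appendix B) has ECG rows for Weeks 12, 36, 60 and 84. Footnotes to the rollover schedules already refer to a predose ECG at Week 12. Nothing in the SAP states an intention to leave these visits out of the rollover ECG summary.

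**Step 5: after the change.** With windows 2–126, 127–210, 211–294, 295–378, 379–462, 463–546, 547–630 and 631 to max(686, date of Week 96 + 14), every one of the 8 ECGs stays in its own window on all 15 permitted days. Retention becomes 8 of 8.

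**The case against.** The best defence is textual. SAP 2.1 says that the data will be presented, not that they will be summarized by visit, and SAP 8.4 places all safety data in individual listings. Read literally, the listings honour the promise. But SAP 8.4 would list these ECGs without any help from section 2.1, so on this reading the commitment adds nothing. The listings would also carry the Table 11-4 visit labels, which do not include Weeks 12, 36, 60 or 84.

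Other points limit the consequence and stand:
- The QTcF threshold analysis uses the worst record, so it loses nothing. No ECG is lost from the database or the listings, and no hypothesis is tested.
- In the by-visit summary, mislabelling arises only when the 24-weekly ECG for that window is missing. The documents do not say how often that happens.
- Rows with IVA-naïve subjects only already occur by design, for example ECG at Week 4 and vital signs at Weeks 2, 4, 8 and 18. The difference here is that four further rows would become so by oversight, against the SAP's own statement.
- Appendix A largely reproduces the protocol schedule, so the missing X there is a matter of tidying.

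**Conclusion.** The SAP is inconsistent as written and Table 11-4 should be corrected. For a rollover subject who completes treatment with visits inside the ±7-day allowance, 4 of 8 scheduled post-Day-1 ECGs (50%) have no analysis row and do not enter the by-visit raw-value and change-from-baseline summaries. Where a 24-weekly ECG is missing, a record 77 to 91 days off target may take its label. A Week 84 ECG can be labelled Week 96 only from day 589 onward; on its scheduled day it falls in Week 72.

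The effect is confined to the by-visit summaries and to visit labels for rollover subjects. The share of all study ECGs affected cannot be given, because the documents do not state how many subjects rolled over. This is a correction that should be made, not a threat to the safety conclusions as a whole.

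**What to change.** In SAP Appendix B, Table 11-4, replace the four rollover ECG windows with the 12-weekly set already used in that table for chemistry, hematology and vital signs:

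| Analysis visit | Target day | Window (study days) |
|---|---|---|
| Week 12 | 84 | 2 to 126 |
| Week 24 | 168 | 127 to 210 |
| Week 36 | 252 | 211 to 294 |
| Week 48 | 336 | 295 to 378 |
| Week 60 | 420 | 379 to 462 |
| Week 72 | 504 | 463 to 546 |
| Week 84 | 588 | 547 to 630 |
| Week 96 | 672 | 631 to max(686, date of Week 96 + 14) |

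From Week 24 onward these match the IVA-naïve ECG windows, so the pooled rows align. Add the X for ECGs at Weeks 12, 36, 60 and 84 to SAP Tables 11-1 and 11-2. If the sponsor does intend these ECGs to be listed only, SAP 2.1 and 8.4.3 should say so, and the pooled table should carry a footnote that those rows contain IVA-naïve subjects only.

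The cost is a table edit in the SAP and the matching change to the windowing program. No new data are needed.
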